## STUDY SUMMARY

TITLE	IntravaScular Ultrasound (IVUS) Imaging During Transvenous LEad Extraction (ISEE)
SHORT TITLE	ISEE
PROTOCOL NUMBER	IRB18-1600
METHODOLOGY	Clinical Trial
SAMPLE SIZE	100 consecutive patients that have been recommended for lead extraction, with at least one lead over 1 year dwell time
STUDY DURATION	1 year
STUDY CENTER(S)	University of Chicago Medicine, Penn Medicine, University of Michigan, Allina Health
OBJECTIVES	The purpose of this study is to evaluate IVUS as a tool for grading the presence of fibrotic adhesions to cardiac pacemaker/defibrillator leads during transvenous lead extraction (TLE).
DIAGNOSIS AND MAIN INCLUSION CRITERIA	Subjects that have been recommended for TLE with at least one transvenous lead over 1 year dwell time.
STUDY PRODUCT	IVUS catheter (Visions® PV.035)
DURATION OF ADMINISTRATION	For the duration of the TLE procedure
STATISTICAL METHODOLOGY	Traditional statistical methods will be employed. The student's T-test will be used for continuous comparisons. Fisher's exact or the Chi-square test will be applied for dichotomous variables. Spearman correlation coefficients will be calculated.

## LIST OF ABBREVIATIONS

CIED	Cardiovascular implantable electronic device
CXR	Chest x-ray
ICD	Implantable cardioverter-defibrillator
ILA	Intravascular lead adherence
INNV	Innominate vein
IVUS	Intravascular ultrasound
PA	Postero-anterior
RA	Right Atrium
SVC	Superior vena cava
TV	Tricuspid valve
TEE	Transesophageal echocardiography
TLE	Transvenous lead extraction

## INTRODUCTION

### BACKGROUND AND RATIONALE

Increased indications for permanent cardiac pacing with biventricular pacing systems and the success of implantable cardioverter-defibrillators (ICD) in improving mortality in patients with ventricular arrhythmias and chronic systolic heart failure, has resulted in a significant increase in the rate of implantation of cardiovascular implantable electronic devices (CIEDs) [1,2]. Unfortunately, there has also been a parallel rise in the rate of CIED infection and lead failure or malfunction with subsequent increase in the need for transvenous lead extraction (TLE) [1,3]. As outlined in the 2017 Heart Rhythm Society (HRS) consensus statement on lead management and extraction, CIED leads should be fully removed in the case of system infection (class I indication), and lead removal is suggested in the case of lead malfunction, fracture, or recall [4]. Some CIED leads can be removed without locking stylets or powered cutting sheaths, and therefore, TLE poses little risk to the patient. However, due to the development of fibrosis on the majority of CIED leads especially within sensitive venous and cardiac structures, more complex procedures are often necessary, requiring the use of laser sheaths or powered cutters to break the lead free from tissue and vascular adhesions. During this procedure, major adverse events can occur that can lead to patient morbidity and mortality. The most common mechanical injury during TLE is a tear in the superior vena cava (SVC) [5]. Though rare, this complication is often devastating and associated with significant morbidity and mortality and almost always requires emergent surgical intervention [4]. A common variable associated with this major complication is the presence of significant intravascular lead adhesion (ILA) or fibrosis [5].

Currently it is difficult to predict the locations and severity of ILA within the SVC or right atrium (RA) giving physicians a significant disadvantage when entering these procedures. Pre-procedure imaging with CXR, CT scan and fluoroscopy have limited utility [6]. While clinical risk factors such as female gender, longer lead dwell time, presence of high voltage coil or existence of multiple leads in the vascular space,

low body mass index (BMI) and younger patient age have all been associated with a greater likelihood of ILA, they are not reliable predictors due to the inherent inter-patient variability in the vascular biology dictating the development of ILA [7,8,9,10].

Phased-array intracardiac echocardiography (ICE) and/or radial-ICE, also known as IVUS, have become important imaging tools in electrophysiology (EP) [11]. It is standard of care to use ICE in many EP procedures [11]. It helps in performing safe trans-septal puncture, aids in identifying important cardiac structures (papillary muscles, pulmonary veins, aortic cusps), and is utilized to monitor for complications (pericardial effusion, clot development, steam pops) [11].

Radial-ICE or IVUS has been utilized during TLE and was found to be a feasible and safe tool to visualize leads in a small study of 25 patients. The authors concluded that radial-ICE evaluation “is safe and feasible in patients with pacing and defibrillating leads before and during transvenous lead removal, offering an excellent visualization of cardiac leads and related areas of adherence. ICE can assist pacing and ICD lead removal and could improve procedure efficacy and safety” [12]. Sadek and colleagues evaluated phased array ICE in 50 patients undergoing TLE. The authors concluded that while phased-array ICE was able to identify areas of binding it was not able to identify binding sites that are high versus low risk of requiring complex extraction techniques. In this study, there were no adverse events noted with using ICE [13]. Radial ICE or IVUS has a number of advantages over phase- array ICE because it can provide a 360° cross-sectional image, allowing better visualization and assessment of ILA.

At the University of Chicago, IVUS is routinely used during TLE. At first, we used it to monitor for complications like the development of pericardial effusion or clots. We quickly realized that it had other uses. Under the following IRB protocol #16-0272 titled “Safety and Outcomes of Electrophysiology Procedures in the Electrophysiology Laboratory at the University of Chicago: A Prospective Registry for Arrhythmia Care”. [name] and I reviewed and collected data on 56 patients who had undergone TLE where IVUS imaging was performed and ILA was identified and quantified. We correlated the degree of ILA seen on IVUS to metrics reflecting the difficulty of TLE (pulses of laser energy delivered and time required to traverse an area of fibrosis or ILA). We found that (1) ILA can be readily visualized, accurately quantified using IVUS, (2) The degree of ILA correlates highly with difficulty of extraction as measured by the time required to traverse and the amount of laser pulses delivered in each vascular segment and (3) IVUS has potential to identify patients who may be at low risk for vascular complications in the SVC-RA region during TLE. No additional complications were found by routinely using IVUS and we noted that there was an added incremental value to clinical predictors of fibrosis. For example, a patient with a low body mass index, a high lead dwell time and a dual coil ICD lead would be expected to have a higher amount of ILA based on clinical factors. We found that these factors were not reliable. In many cases, IVUS was able to demonstrate minimal ILA, This finding helped guide laser sheath use and the need for placing the Philips rescue balloon. In contrast, a patient with risk factors predicting low ILA may have IVUS findings indicating the opposite. This type of finding would help in determining whether the extraction should be approached from below (femoral work station) or not performed using laser (e.g. refer to surgery). Our work was presented in the Philips Imaging Symposium in July 2018 in Philadelphia. Our data was very well received by our EP colleagues, and this led us to initiating a larger multi-center study to validate our findings.

Therefore, the purpose of this study is to prospectively evaluate intravascular ultrasound (IVUS) imaging as a tool for grading the presence and characterization of ILA to cardiovascular implantable electronic device (CIED) leads during transvenous lead extraction (TLE) procedures in a multi-center study. IVUS should identify the location and severity of these adhesions, which we will then correlate to difficulty of the extraction procedure using metrics like pulses of laser energy delivered and time required to traverse an area of fibrosis or ILA. We will be focusing primarily on the section from innominate vein (INNV) down through the superior vena cava (SVC) to the right atrium.

Currently, the Visions® PV.035 IVUS catheter is designed for use in the evaluation of vascular morphology in blood vessels of the peripheral vasculature [Appendix A]. It is commonly used during interventional cardiology and radiology procedures and has a solid safety profile [14-19]. In a large study of 227 patients, the Visions® PV.035 IVUS catheter was used to assess pelvic vein insufficiency. There were no adverse events related to IVUS imaging [14]. Two other studies of 117 and 104 patients respectively, found that imaging with the Visions® PV.035 IVUS catheter was safe and not associated with any adverse events [15,16]. Three other studies using the Visions® PV.035 IVUS catheter found similar results [17,18,19]. In all of these studies, the Visions® PV.035 IVUS catheter was used to image peripheral veins. In our proposed study, we wish to use IVUS to image leads in venous structures (SVC, INNV) and the SVC-RA junction. The IVUS catheter will need to be inserted through a sheath inserted in the right or left femoral vein and pass through the RA to reach the regions of interest which constitutes an “off-label” use of the product. This “off-label” use of the IVUS catheter is standard clinical practice in the University of Chicago EP cath lab. There were no adverse events seen with use of IVUS in our cohort of 56 patients that Drs. [name] and I studied from the EP registry data. Based on the published literature supporting the safety of the Visions® PV.035 IVUS catheter and our own experience, we believe that using IVUS for this purpose provides a non-significant risk to patients.

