## **SUBJECT SELECTION AND WITHDRAWAL**

### SITES:

Subjects selected for study will be recruited from 4 sites: University of Chicago Medicine, Chicago, IL; Penn Medicine, Philadelphia, PA; University of Michigan, Ann Arbor, MI; Allina Health, St.Paul, MN

Eligibility: Patients that have been recommended for lead extraction are eligible for enrollment.

A total of 100 eligible patients will be enrolled in the study. Twenty-five patients will be enrolled at each site which will allow 2 things: (1) the operator will first become comfortable with interpreting the images obtained from IVUS (5 patients) and (2) imaging from the remaining 20 patients will help reinforce understanding of the grading scale [25 patients x 4 sites = 100 patients]. Assuming a Pearson correlation sample size calculation:

- Power: 80%
- Alpha Value: 5%
- Baseline  $H_0$  Correlation: 0.50
- Alternative Correlation: 0.70
- Drop-Out Rate: 20%
- Sample Size Calculation: 100 patients

See Appendix D for further information.

Inclusion:

- Patients at least 21 years of age
- Patients with at least one lead over 1 year dwell time requiring extraction

Exclusion:

- Inability of patient capacity to provide consent for themselves either due to medical or psychiatric comorbidity
- Venous occlusion to the extent that the IVUS catheter cannot pass
- Leads < 1 year dwell time requiring extraction

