## **STATISTICAL PLAN AND CONSIDERATIONS**

Using Stata statistical software (StataCorp LP, College Station, Texas), ILA grades will be correlated to the time required and amount of laser pulsations delivered to traverse each vascular segment. Spearman correlation coefficients will be calculated. The student's T-test will be used for continuous comparisons. Fisher's exact or the Chi-square test will be applied for dichotomous variables.

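### The study sets out to validate the lead site's own findings, but that site supplies a quarter of the patients and the planned correlations make no allowance for site

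*Combined protocol and SAP*

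**What the plan says.** The Background and Rationale section reports that the lead-site team "collected data on 56 patients who had undergone TLE where IVUS imaging was performed". Among the findings it lists is this one: "The degree of ILA correlates highly with difficulty of extraction as measured by the time required to traverse", and likewise with the laser pulses delivered in each segment. It then says that this work led to "initiating a larger multi-center study to validate our findings". It also states: "At the University of Chicago, IVUS is routinely used during TLE".

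Under Subject Selection and Withdrawal, Sites, the lead site is the first of four recruiting sites. "Twenty-five patients will be enrolled at each site", for a total of 100. The first five patients at every site are set aside for the operator to get used to reading the images.

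The Statistical Plan and Considerations section relates adhesion grade to traverse time and laser pulses for each vascular segment: "Spearman correlation coefficients will be calculated". It adds t-tests and Fisher's exact or chi-square tests. Site is not mentioned. Appendix D sizes the study as one sample with one correlation: null 0.50, alternative 0.70, two-sided alpha 0.05, 80 evaluable, 100 enrolled after 20% dropout.

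The correlation is Aim 2 and a secondary endpoint. The ability to image adhesion is Aim 1 and the primary endpoint.

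**The concern.** A validation is most persuasive where the finding did not originate. Here a quarter of the data come from the originating site, which already used the technique routinely, and nothing in the plan separates that quarter from the rest.

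Site differences are foreseeable:

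- Grade is the operator's own judgement of how freely a lead moves, and no central or blinded reading is described.
- Extraction tools and laser settings are recorded but not standardised, so time and pulse counts can differ between sites for reasons unrelated to adhesion.

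If sites differ on average in both grade and difficulty, a correlation over all patients mixes the within-site relation, which is the one of interest, with the between-site pattern. It may come out too high or too low. Separately, if the relation is truly stronger at the lead site, the pooled value overstates what the other centres would see.

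**Working it through.** **1. The plan's own figure.** By Fisher z, N = ((1.960 + 0.842) / (atanh 0.70 − atanh 0.50))² + 3. With atanh 0.70 = 0.867 and atanh 0.50 = 0.549, the difference is 0.318 and N = 80.6. Power at 80 is Φ(0.318 × √77 − 1.960) = Φ(0.830) = 0.797, or 0.800 with the small-sample bias term, against the stated 0.80092. Dropout inflation is 80 / 0.80 = 100. The stated figures reproduce, and the calculation has no site component.

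**2. Lead-site share.** 25 / 100 = 25%. After 20% dropout there are 25 × 0.80 = 20 evaluable per site and 75 × 0.80 = 60 at the other three.

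**3. Effect of unequal site means.** The documents give no site differences, so these are assumptions: four equal, equally spaced sites and a within-site Pearson correlation of 0.50. The matching Spearman value is (6/π) × arcsin(0.25) = 0.48, which is the no-shift baseline. If g is the gap between the extreme sites in within-site SD units, the variance of the site means is v = 5g²/36. The pooled Pearson value is (0.50 + v)/(1 + v) when grade and difficulty shift together, and (0.50 − v)/(1 + v) when they shift oppositely. The Spearman columns are from simulation.

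| Gap g | SD of site means | Pearson, together | Pearson, opposite | Spearman, together | Spearman, opposite |
|---|---|---|---|---|---|
| 0.25 | 0.09 | 0.504 | 0.487 | 0.49 | 0.47 |
| 0.50 | 0.19 | 0.517 | 0.450 | 0.50 | 0.43 |
| 0.67 | 0.25 | 0.529 | 0.412 | 0.51 | 0.40 |
| 1.34 | 0.50 | 0.600 | 0.200 | 0.59 | 0.18 |

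If only the lead site is shifted, by 0.25 to 0.5 SD upward on both variables, the pooled Spearman is 0.49 to 0.51. With a three-level grade like the plan's, the within-site value is about 0.43 to 0.44. Site means with an SD of 0.25 or 0.5 then give 0.47 or 0.54 together, and 0.36 or 0.16 oppositely.

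**4. Effect on a test against 0.50** (Pearson basis, 4 × 20 evaluable, true within-site value 0.50). Rejection in favour of a higher correlation should be 2.5%. With only the lead site higher on both variables, it is 4.9% at 0.5 SD and 17% at 1 SD. With site means at −0.75, −0.25, 0.25 and 0.75 SD on both variables, it is 35%. A site-stratified Fisher z keeps two-sided error at about 5% in all these cases.

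**5. Effect of a stronger relation at the lead site.** If the lead-site correlation is 0.70 and the others are 0.50, the pooled value is (20 × 0.70 + 60 × 0.50)/80 = 0.55, and rejection in favour of a higher correlation is 9.5%.

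**6. What three sites can show.** At 60 evaluable, power for 0.50 against 0.70 is Φ(0.318 × √57 − 1.960) = Φ(0.441) = 0.67. At r = 0.70 the 95% CI is tanh(0.867 ± 1.96/√57), or 0.54 to 0.81. For one site with 20 evaluable it is tanh(0.867 ± 1.96/√17), or 0.37 to 0.87.

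**The case against.** Including the originating centre in a larger multi-centre study is not an error, and the protocol does not claim external or independent validation. A reader might infer that this is no independent validation at all. The documents do not support that: recruitment is prospective, nothing says the 56 earlier patients are counted among the 100, and 75% of patients come from elsewhere.

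A reader might also infer that the other three sites are new to the method. The protocol does not say so. Its Overall Study Design section describes all investigators as expert in extraction and in intracardiac echocardiography, and the five familiarisation cases apply to every site, including the lead site.

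Nor would a pooled correlation undermine Aim 1, since imaging is a different endpoint.

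Pooling itself is inferred from the one-sample calculation and the silence on site. Several coefficients are planned, for time, for pulses and by segment.

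On size, modest site gaps move the coefficient little. The large shifts need extreme sites about 1.3 SD apart and shifts perfectly aligned or opposed. If grade and difficulty shift independently, with site means of SD 0.25, the average pooled Spearman is 0.46, a small attenuation.

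All of this stands, and it limits the strength of the point. It does not supply what is missing: no planned analysis would show whether site mattered, or what the three other centres found.

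**Conclusion.** The point holds as a cheap improvement to the analysis. The pooled result is a partly external validation, and an analysis that ignores site can be biased in either direction. Against a baseline Spearman of 0.48, the movement is about −0.05 to +0.02 if the extreme sites differ by up to 0.5 SD. It is about −0.30 to +0.11 if they differ by 1.34 SD. A shift confined to the lead site, of up to 0.5 SD upward on both variables, adds at most about 0.03. These sizes rest on assumed site differences and a normal model.

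The correlation affected is a secondary endpoint, although it is the only one the study is sized on. Aim 1 mentions five centres while the design lists four; a fifth site would change the lead site's share.

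**What to change.** In the Statistical Plan and Considerations section:

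- Make the main correlation site-stratified, either as a partial Spearman given site or by ranking within site and then pooling.
- Report the primary imaging endpoint for each site.
- Repeat both without the lead site, as a sensitivity estimate with its 95% CI and not as a test.
- Give single-site correlations as description only.

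Stratifying removes the effect of unequal site means. The three-site estimate deals with a stronger relation at the lead site, which stratifying alone does not.

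The cost is a few lines of code and no extra patients or procedures. The downside is precision. The three-site estimate has about 60 evaluable patients and power of about 0.67 for 0.50 against 0.70, or about 0.62 if it is itself stratified with n − 3 per site. Stratifying all four sites takes power at 80 evaluable from 0.80 to about 0.75 by that formula, though simulation puts it at about 0.80. These figures use the plan's Pearson basis; a Spearman analysis would do somewhat worse.

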## OBJECTIVES

We hypothesize that:

IVUS imaging will provide incremental value beyond clinical factors in identifying vascular adherence

### Specific Aims:

Aim 1: Experienced operators at 5 major lead management medical centers will be able to image ILA using IVUS during TLE

Aim 2: ILA will be correlated to metrics of TLE difficulty

Aim 3: The incremental value of IVUS will be assessed systematically in identifying patients at low risk of developing a vascular tear in the SVC-RA region

## **PRIMARY ENDPOINTS**

1. Ability of IVUS to image ILA

## **SECONDARY ENDPOINTS:**

1. Correlate ILA grade to metrics reflecting the difficulty of TLE
2. Fluoroscopy time of the procedure, number and type of extraction sheaths used, and changes in tooling type during the procedure.

### Primary safety endpoints:

1. Major complications during lead extraction as defined by the 2017 HRS expert consensus statement on cardiovascular implantable electronic lead management and extraction [4]. These include death, cardiac avulsion, vascular laceration, and pericardial effusion, requiring intervention during the extraction procedure.

## **STUDY DESIGN**

### OVERALL STUDY DESIGN:

This study will be conducted at 4 major institutions (University of Chicago Medicine, Penn Medicine, University of Michigan, Allina Health) that specialize in TLE. The investigators in this study are electrophysiologists with expertise in TLE and imaging using ICE. All adult patients over the age of 21 years scheduled to undergo lead TLE for any indication will be eligible to participate as long as the lead dwell time is greater than 1 year.

Duration of study: 1 year

## **SUBJECT SELECTION AND WITHDRAWAL**

### SITES:

Subjects selected for study will be recruited from 4 sites: University of Chicago Medicine, Chicago, IL; Penn Medicine, Philadelphia, PA; University of Michigan, Ann Arbor, MI; Allina Health, St.Paul, MN

Eligibility: Patients that have been recommended for lead extraction are eligible for enrollment.

A total of 100 eligible patients will be enrolled in the study. Twenty-five patients will be enrolled at each site which will allow 2 things: (1) the operator will first become comfortable with interpreting the images obtained from IVUS (5 patients) and (2) imaging from the remaining 20 patients will help reinforce understanding of the grading scale [25 patients x 4 sites = 100 patients]. Assuming a Pearson correlation sample size calculation:

- Power: 80%
- Alpha Value: 5%
- Baseline  $H_0$  Correlation: 0.50
- Alternative Correlation: 0.70
- Drop-Out Rate: 20%
- Sample Size Calculation: 100 patients

See Appendix D for further information.

Inclusion:

- Patients at least 21 years of age
- Patients with at least one lead over 1 year dwell time requiring extraction

Exclusion:

- Inability of patient capacity to provide consent for themselves either due to medical or psychiatric comorbidity
- Venous occlusion to the extent that the IVUS catheter cannot pass
- Leads < 1 year dwell time requiring extraction

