Prior to pocket access, the IVUS catheter is inserted through a right or left femoral venous approach and advanced under fluoroscopic guidance to the RA. If the pacemaker lead entry is in left pectoral region, imaging will begin from the innominate vein using the medial end of left clavicle as the origin, registered under fluoroscopy. If the pacemaker leads start from right pectoral region, then imaging begins in the cranial portion of SVC, using the medial end of the right clavicle as origin, registered under fluoroscopy. A 0.32 guidewire can help with IVUS catheter manipulation if necessary.

Based on fluoroscopy alone, in left sided device implants, the chest will be divided into 3 zones: Zone 1 includes the area between the head of the clavicle and the innominate vein; zone 2 includes the area between the innominate vein to SVC-RA junction and zone 3 includes the area between the SVC-RA junction through to the mid RA. In right sided device implants, zone 1 includes the area between the head of clavicle to the SVC-RA junction; zone 2 includes SVC-RA junction through to the mid RA.

From there the physician retracts the IVUS catheter through the SVC to the RA in a “survey” run, looking for areas of ILA between the lead and the SVC wall in the previously outlined zones. He/she will also note the presence of lead-on-lead binding. At least one representative image from each zone will be recorded, labelled and saved on the IVUS console. Fluoroscopic images of IVUS catheter position at each site of image recording will be saved and labelled. Using the following scale, grading of ILA in each zone of interest, based on relative motion of lead will be performed:

- i. Grade 1: Freely mobile, Rarely adjacent to vasculature
- ii. Grade 2: Restricted mobility, Frequently adjacent to vasculature
- iii. Grade 3: Immobile, Always adjacent to vasculature
- iv. Grade L, added to number: Lead-to-lead binding

If no ILA is seen, the extraction procedure commences.

If physician identifies locations of adhesions, he/she returns the IVUS catheter to those locations to evaluate severity of adhesion and quantify adhesions based on standardized grading scale which is outlined above. Once all adhesions are evaluated, the extraction procedure commences and the physician gains pocket access and prepares the lead for extraction. The subjective amount (small, moderate, large) of pocket calcification needs to be noted.

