The physician begins the extraction until the leads are free through the subclavicular space. At this point, a second run of IVUS imaging is done focusing on areas of highest adhesion seen in the initial imaging. These IVUS images will be collected and saved. When adhesion areas are located, traction is applied to lead of interest to watch the dynamic response of lead movement, then regraded accordingly. Both grades, initial and secondary, should be recorded. The highest grade of adhesion seen in the zone of interest is recorded for that lead. Once this is done, the IVUS catheter may or may not be removed during the extraction procedure. It may left in the low RA to monitor for pericardial effusion development. Added imaging protocol should add 10 minutes to the overall procedure.

During the extraction, the following information needs to be recorded: Laser pulse number of lasing per zone, number of handle pulls for mechanical sheath and time of progression through zone of interest.

Once the extraction is completed, the following data will be collected:

Procedural Data to Record:

1. Length of Procedure (Patient-on-table to wheel-out)
2. Order of leads extracted
3. IVUS Procedure
  - a. Length of imaging time
  - b. Location of adhesions (images will be captured and collected for the study)
  - c. Grading of adhesion in zone of interest, based on relative motion of lead:
    - i. Grade 1: Freely mobile, Rarely adjacent to vasculature
    - ii. Grade 2: Restricted mobility, Frequently adjacent to vasculature
    - iii. Grade 3: Immobile, Always adjacent to vasculature
    - iv. Grade L, added to number: Lead-to-lead binding
4. Length of Extraction (Opening pocket to start of re-implantation, if applicable)
5. Extraction tools
  - a. Laser, Mechanical, Dilating Sheath
  - b. Starting sheath size
  - c. Change of sheath size, settings (40 v. 80Hz), and type
  - d. Use of Outer Sheath
  - e. Switching of leads to extract
6. Location of adhesions felt by extractor
7. Operator rating about ease of sheath advancement in each zone (zones 1-3):
  - a. None – removed without sheaths
  - b. 0 – advanced without power assistance
  - c. 1 – Power assistance but easily advanced
  - d. 2 – Power assistance with effort

8. Laser pulse number of lasing per segment
9. Number of handle pulls for mechanical sheath
10. Time of progression through zone of interest
11. Pocket calcification (Y/N)
12. Clinical Outcome Data:
  - a. Extraction procedural success, as defined above

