#### Summary Statements

A sample size of 80 achieves 80% power to detect a difference of -0.20000 between the null hypothesis correlation of 0.50000 and the alternative hypothesis correlation of 0.70000 using a two-sided hypothesis test with a significance level of 0.05000.

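### The only power figure (80% at 80 evaluable patients) is for a Pearson test of 0.50 against 0.70, while the plan only calculates Spearman coefficients, makes no comparison with 0.50, and leaves grade, metric and pairing unit open

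*Combined protocol and SAP*

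**What the plan says.** The sample-size paragraph under Subject Selection and Withdrawal (Sites) opens with "Assuming a Pearson correlation sample size calculation". It lists 80% power, 5% alpha, a null correlation of 0.50, an alternative of 0.70, 20% drop-out and 100 patients. Appendix D gives the software output: "A sample size of 80 achieves 80% power to detect a difference of -0.20000 between the null hypothesis correlation of 0.50000" and an alternative of 0.70, two-sided at 5%. Its definitions count N in subjects, which means one pair per patient. No other power statement appears.

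Statistical Plan and Considerations describes the analysis: "ILA grades will be correlated to the time required and amount of laser pulsations delivered to traverse each vascular segment". Both it and the Study Summary state that "Spearman correlation coefficients will be calculated". Neither mentions 0.50, a test of the coefficient or a confidence interval.

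The Procedure section sets the data structure:

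- **Grade.** "Using the following scale, grading of ILA in each zone of interest, based on relative motion of lead will be performed". The scale has three ordered levels, plus a suffix for lead-to-lead binding. A second run regrades under traction, and both grades are kept.
- **Lead.** "The highest grade of adhesion seen in the zone of interest is recorded for that lead".
- **Zone.** Left-sided implants have three zones. Right-sided implants have two, and there "zone 2 includes SVC-RA junction through to the mid RA", which is the stretch called zone 3 on the left.
- **Metrics.** The data to record are "Laser pulse number of lasing per zone, number of handle pulls for mechanical sheath and time of progression through zone of interest". Tools include laser, mechanical and dilating sheaths, and the operator rating allows for leads removed without any sheath.

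Correlating grade with difficulty is a secondary endpoint. The primary endpoint, ability to image adhesions, has no sample-size calculation.

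**The concern.** The number of patients rests on a hypothesis that the statistical plan does not say it will test. Three things differ between the sizing and the analysis:

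- **Statistic.** Sizing uses Pearson, which assumes two continuous, jointly normal variables. The analysis uses Spearman with a three-level grade.
- **Null value.** Sizing uses 0.50. The plan states none.
- **Pair.** Sizing uses one per patient. The data can supply several per patient, by zone and by lead, with two grades and two metrics.

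Two consequences follow. First, a reader who takes 80% as the power of the correlation analysis is misled, by an amount and in a direction that depend on unstated choices. Second, with several candidate coefficients and no reference value, a moderate one could be presented as supportive although it would not meet the hypothesis that justified 100 patients.

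**Working it through.** **1. Reproduce the stated figure.** Inputs from Appendix D: null 0.50, alternative 0.70, two-sided alpha 0.05, N = 80, drop-out 20%.

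- Exact distribution of the sample Pearson coefficient: critical values 0.318 and 0.650; power 0.80092 at N = 80 and 0.7958 at N = 79. This matches Appendix D to five decimals.
- Fisher z check: atanh(0.70) − atanh(0.50) = 0.8673 − 0.5493 = 0.3180. Then 0.3180 × √77 = 2.790, and Φ(2.790 − 1.960) = 0.797.
- Enrolment: 80 / (1 − 0.20) = 100.

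The calculation is correct for its own test.

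**2. Same hypotheses, Spearman, 80 independent pairs, grade treated as continuous.** Power ≈ Φ{[0.3180·√77 − 1.96·√v₀] / √v₁}.

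- With v₀ = v₁ = 1.06: Φ(2.790/√1.06 − 1.96) = Φ(0.750) = 0.773.
- With the Bonett-Wright variance 1 + ρ²/2, v₀ = 1.125 and v₁ = 1.245: Φ[(2.790 − 1.96 × 1.061)/1.116] = Φ(0.638) = 0.738.

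**3. Three-level grade.** The documents give no grade split. The simulation cuts one variable of a bivariate normal pair into three grades and ignores the lead-to-lead suffix. Assumed splits: equal thirds, 50/30/20, 40/40/20, 60/30/10. N = 80, one pair per patient.

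| Reading of 0.50 and 0.70 | Test held at 2.5% one-sided | Bonett-Wright interval |
|---|---|---|
| Both are Spearman values for the graded data | about 75–79% (0.758–0.771 with 40,000 replicates) | about 72–74% |
| Both refer to the underlying continuous scale | about 50–62% | about 47–58% |

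On the first reading, Bonett-Wright has a one-sided error of only about 2%, so part of its lower power is conservatism. On the second, the graded coefficients shrink to 0.413–0.443 and 0.586–0.632, which narrows the gap to be detected. A more skewed split (70/20/10) gives about 46% with the calibrated test.

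**4. Number and independence of pairs** (graded 0.70 against 0.50, test held at 2.5% one-sided).

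- Fewer pairs, for example laser cases only: 0.63–0.64 at an assumed 60 pairs and 0.43–0.45 at an assumed 40.
- Two or three zones pooled per patient, 80 patients, assumed within-patient correlation 0.2–0.8: 0.89–1.00, above the stated 80%.
- Three pooled zones analysed with Bonett-Wright as if independent: one-sided error 2.2–2.4% at within-patient correlation 0.2, 3.6–3.9% at 0.5 and 7.1–7.5% at 0.8. Clustering matters when it is strong.

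**5. What the missing reference value allows.** Against 0.50 at N = 80, the observed coefficient must reach tanh(0.5493 + 1.96/√77) = 0.648 by Fisher z, or 0.662 by Bonett-Wright. A coefficient of 0.55 falls short, yet the plan has no rule that shows this. Tested against zero, a true Spearman coefficient of 0.50 would have over 99% power.

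**6. How many coefficients.** For left-sided implants, 3 zones × 2 metrics × 2 grades gives up to 12, before leads are separated. This is an upper limit, because the second run concentrates on the areas graded worst on the first. None is named as main.

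**The case against.** The strongest reply is that the correlation is a secondary endpoint, the plan sets no pass/fail rule for it, and sizing a Spearman analysis with a Pearson formula is a common approximation. On the one-pair reading it costs only about 1–5 points with a calibrated test. This largely stands: it limits the weight of the point and shows that the change of coefficient alone is a small matter. It does not explain why the 0.50 used for sizing is absent from the analysis, nor supply the missing grade, metric and unit. If the analysis is meant to be descriptive, the 80% describes nothing that is planned.

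Two further points stand. The plan does name a level, each vascular segment, so the unit is not wholly unspecified; what is open is patient, lead or zone within it, and pooling. The plan is also silent on 0.50 rather than contrary to it.

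A reader might infer that the study is underpowered. The documents do not support that. The lower figures rest on assumed grade splits and pair counts, and pooling zones could take power above 80%. Nor is there support for putting 0.70 on the continuous scale and 0.50 on the graded one, which would give much lower figures still; nothing in the documents mixes the scales.

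**Conclusion.** The point holds as a mismatch between sizing and analysis, and should be corrected. The stated 80% is right for a two-sided Pearson test of 0.50 against 0.70 with one independent pair per patient, and it is not the power of the analysis described.

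The size depends on choices that the plan leaves open. At 80 independent pairs, power is about 75–79% if both values are Spearman coefficients for the graded data (72–74% with Bonett-Wright), and about 50–62% if both refer to an underlying continuous scale. Pooled zones may exceed 80%; restriction to laser cases would lower it. Every figure for the graded data rests on assumed splits, and the pooled ones also on an assumed within-patient correlation.

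A reader might also infer an arithmetic error, or a threat to the primary endpoint. Neither follows: Appendix D reproduces exactly, and the primary endpoint is not the one that was sized.

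**What to change.** Text only; enrolment stays at 100.

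**Statistical Plan and Considerations**

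- Name one main correlation: one grade (initial or under traction), one metric chosen by the investigators, and one unit. One pair per patient is closest to the sizing. If a segment is used, name the anatomy rather than the zone number.
- State how cases without the chosen metric are handled. Pulses exist only where laser was used. For time, say whether it is recorded for leads removed without sheaths.
- Report the Spearman coefficient with a 95% confidence interval and compare that interval with the 0.50 used for sizing. This is a reference value for a secondary endpoint, not a criterion for the trial as a whole.
- Call the other correlations supportive.
- If zones or leads are pooled, account for clustering within patient and check the error rate of the chosen method. A patient-level bootstrap on the Fisher z scale gave a one-sided error of 3.2–3.7% with three zones, so it should not be assumed to hold 2.5%.

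**Sample-size paragraph and Appendix D**

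- Replace the 80% with the power of that Spearman analysis at the expected number of evaluable pairs.
- State the interval method, the assumed grade split, the scale to which 0.50 and 0.70 refer, and, if pairs are pooled, the within-patient correlation.

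The cost is a few sentences and one recalculation. On the one-pair reading, with both values taken as graded Spearman coefficients, the stated power becomes slightly less favourable.
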